7.3.2 Physical and Neurological Examinations

Physical and Neurological examination data will be summarized separately using descriptive statistics by baseline and post-baseline visit, for each component. Listings for both physical and neurological examinations will be provided.

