Protocadherin (PCDH)19- female-pediatric epilepsy (FPE), also known as PCDH19 female-limited epilepsy (FLE) or epilepsy in females with mental retardation (EFMR), is a serious epileptic syndrome characterized by early-onset cluster seizures, cognitive and sensory impairment of varying degrees, and behavioral disturbances in some individuals.¹ This disorder is associated with a mutation of the PCDH19 gene, the gene that encodes for protocadherin19 on the X chromosome.^{2,3} The mechanism by which this mutation contributes to the development of epilepsy and intellectual impairment is not fully understood, however protocadherin19 is a transmembrane protein of calcium-dependent cell-cell adhesion molecules that is strongly expressed in neural tissue (e.g., hippocampus, cerebral cortex, thalamus, amygdale), and which appears to be related to synaptic transmission and formation of synaptic connections during brain development.³ Research suggests impairment of GABAergic signaling both at the agonist and receptor levels is present in girls with PCDH19 mutations and pediatric-onset epilepsy.⁴

The hallmark characteristics of PCDH19-FPE are clusters of seizures which start in infancy or early childhood often associated with fever or immunization.⁵⁻⁷ Patients with PCDH19-FPE may experience individual seizures in addition to clusters and multiple seizure types. In some patients, seizures improve as patients reach puberty, possibly due to increased endogenous levels of progesterone and allopregnanolone.⁸⁻¹⁰

Background on CDKL5 Disorder

CDKL5 disorder or CDKL5 stands for cyclin dependent kinase like 5, and is located on the X chromosome. The CDKL5 gene was previously called STK9. CDKL5 is a rare X linked genetic disorder that results in early onset, difficult to control seizures, and severe neuro-developmental impairment. ¹⁹

Most of the children affected by CDKL5 present with irritability in the perinatal period, early epilepsy, hand stereotypies, severely impaired psychomotor development and severe hypotonia. In contrast to classical Rett syndrome they also may have absence of a classic regression period, poor eye contact, generally normal head circumference and other growth parameters and relative absence of autonomic dysfunction. ¹⁹

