Ganaxolone has been studied in 5 studies of pediatric seizure disorders in children aged 4 months through 15 years. Genotyping was not performed in any of these trials. Four openlabel studies tested ganaxolone oral suspension at doses up to 36 mg/kg/day in subjects with history or current infantile spasms plus other seizure types including focal and generalized tonic-clonic, resistant to available medications. Across the four studies, approximately two thirds of subjects experienced some improvements in seizures and one third of subjects in these open-label investigations experienced improvements of 50% or greater from baseline seizure frequency. A double-blind, placebo controlled partial crossover trial of ganaxolone in infants (N=57) with infantile spasms did not show a statistically significant reduction in spasms between treatment groups over the 8-10 day treatment period, though only 18 subjects were exposed to placebo. Fifty-four subjects entered the long term open-label extension study, where 25% were recorded as seizure-free on the video EEG at study endpoint.

Most of the adverse events reported in the clinical development program were mild or moderate in severity, dose-related, resolved upon treatment discontinuation, and expected based on ganaxolone pharmacology. The most common adverse events across clinical trials are dizziness, fatigue and somnolence. The adverse event profile of ganaxolone in pediatric studies is similar to that seen in adults, without evidence of unique, clinically meaningful adverse events specific to the pediatric population. Adult and pediatric subjects in open label extension studies to the epilepsy trials have been dosed with ganaxolone for > 2 years (a few children as long as 4 years) with no new adverse events reported as compared to the controlled trials. Three deaths have been reported in the program, none related to ganaxolone.

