7.2 CLINICAL LABORATORY PARAMETERS

Laboratory assessments include hematology, clinical chemistry, and urinalysis:

- Clinical Chemistry: Total Bilirubin, Aspartate Aminotransferase (AST), Alanine Aminotransferase (ALT), Blood Urea Nitrogen (BUN), Glucose, Potassium, Sodium, Calcium, Alkaline Phosphatase, Chloride, Creatinine, Carbon Dioxide (CO₂).
- Hematology: Hemoglobin, Hematocrit, Erythrocytes, Leukocytes + differential, Thrombocytes (platelet count).
- Urinalysis: pH, Color, Transparency, Specific Gravity, Urobilinogen, Ketones, Protein, Glucose

All laboratory parameters will be presented in SI units. Quantitative results (including actual value and change from baseline) will be summarized using descriptive statistics by baseline and

post-baseline visit for each laboratory test group above. Laboratory test results were evaluated as normal, abnormal (not clinically significant) or abnormal (clinically significant). The number and percentage of subjects of each category will be summarized by baseline and post-baseline time point for each parameter.

All laboratory data will be included in the listings. A pregnancy listing will be provided separately.

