7.3.3 ECG

The 12-lead ECG parameters including value and changes from baseline will be summarized using descriptive statistics. ECG results were interpreted as normal, abnormal (not clinically significant) or abnormal (clinically significant). The number and percentage of subjects of each category will be summarized by baseline and post-baseline visit.

Subject listing will be provided. SI units will be used for both summarization and data listings. The critically significant abnormalities will also be flagged in data listings.

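### The examination, ECG-interpretation and laboratory-category tables are by visit only, so they cannot show how many children became newly abnormal; add baseline-by-worst shift tables

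*SAP*

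**What the plan says.** For the examinations, SAP 7.3.2 plans this: "Physical and Neurological examination data will be summarized separately using descriptive statistics by baseline and post-baseline visit, for each component". It adds: "Listings for both physical and neurological examinations will be provided". It mentions neither a change from baseline nor a flag in the listing.

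For the ECG, SAP 7.3.3 has two parts. The numeric part is tied to baseline: "The 12-lead ECG parameters including value and changes from baseline will be summarized using descriptive statistics". The interpretation (normal, abnormal not clinically significant, abnormal clinically significant) is not: "The number and percentage of subjects of each category will be summarized by baseline and post-baseline visit". The section also says: "The critically significant abnormalities will also be flagged in data listings".

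For the laboratory, SAP 7.2 summarizes numeric values and their changes from baseline. The same three-level evaluation is handled by marginal counts: "The number and percentage of subjects of each category will be summarized by baseline and post-baseline time point for each parameter". SAP 7.3.1 does likewise for the low/normal/high classification of vital signs.

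SAP 2.3 restricts by-visit summaries to scheduled visits, and SAP 7 sends unscheduled assessments to the listings. No shift table or newly-abnormal count appears anywhere in the SAP.

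**The concern.** Safety and tolerability is the secondary objective, and the study is uncontrolled. The comparison available is each child against his or her own baseline, which SAP 7 defines. The SAP makes that comparison for numeric laboratory, vital-sign and ECG values, and it counts children whose weight changes by 7% or more. It does not make it for the categorical results.

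The examinations are most affected because they have no numeric summary behind them. They are also close to the effects expected of the drug. The protocol's introduction says: "The most common adverse events across clinical trials are dizziness, fatigue and somnolence". The same introduction describes most children with CDKL5 disorder as having "severely impaired psychomotor development and severe hypotonia", so a substantial rate of neurological abnormality at entry is a fair inference. Where many children start abnormal, few are at risk of becoming newly abnormal, and a stable percentage says little about those few.

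At stake is whether the report's tables can answer a basic safety question: of the children normal at baseline, how many became abnormal on drug?

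**Working it through.** The documents give no figure on this point, so there is none to reproduce. The check is what two marginal counts can and cannot determine.

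**Inputs.** Cohort size n = 10, from SAP 1.3.3 (up to 10 planned per cohort). The numbers abnormal at baseline (b) and at a visit (p) are illustrative, because the documents give no baseline rate. The SAP does not say how examination components are categorized; I assume normal/abnormal. The same n children are taken as assessed both times.

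**Bounds.** The count at a visit satisfies p = b + new − resolved. With resolved between 0 and b, and new at most n − b, the number newly abnormal lies between max(0, p − b) and min(p, n − b).

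| b | p | Newly abnormal | Normal at baseline |
|---|---|---|---|
| 0 | p | exactly p | 10 |
| 3 | 3 | 0 to 3 | 7 (0–43%) |
| 5 | 5 | 0 to 5 | 5 (0–100%) |
| 5 | 6 | 1 to 5 | 5 (20–100%) |
| 8 | 8 | 0 to 2 | 2 (0–100%) |

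**How often the count shows no rise.** Assume each child normal at baseline becomes abnormal with probability 0.3, and each abnormal child resolves with probability r, independently. Then new ~ Binomial(10 − b, 0.3), resolved ~ Binomial(b, r), and P(at least one new) = 1 − 0.7^(10−b). The quantity wanted is P(new ≥ 1 and new ≤ resolved) / P(new ≥ 1).

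| b | P(new ≥ 1) | No rise given new, r = 0.3 | No rise given new, r = 0.1 |
|---|---|---|---|
| 2 | 0.942 | 0.127/0.942 = 13% | 0.041/0.942 = 4% |
| 5 | 0.832 | 0.468/0.832 = 56% | 0.174/0.832 = 21% |
| 8 | 0.510 | 0.463/0.510 = 91% | 0.256/0.510 = 50% |

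For b = 8 and r = 0.3 by hand: 0.42 × (1 − 0.7^8) + 0.09 × (1 − 0.7^8 − 8 × 0.3 × 0.7^7) = 0.42 × 0.942 + 0.09 × 0.745 = 0.463.

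**Across visits.** The schedule has five post-baseline examination visits in the 26 weeks (Visits 3 to 7). If nobody is abnormal at baseline and one child is abnormal at each visit, the tables fit anything from 1 child to 5 different children. By-visit counts cannot say which.

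**Changing denominators.** Missing data are not imputed (SAP 2.5), and percentages use non-missing subjects (SAP 12.1, item 6). After dropout, the children counted at baseline and at a visit can differ, which loosens the bounds further.

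**Unscheduled visits.** Protocol 9.5.5.12 includes examinations and laboratory samples at dose-escalation visits, which are required after escalation above 54 mg/kg/day or 1500 mg/day. Unless a scheduled visit doubles as one, SAP 2.3 keeps its findings out of the by-visit tables.

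**The case against.** The strongest reply is that the within-child comparison already exists elsewhere.

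- **Numeric change.** ECG parameters and quantitative laboratory results have change-from-baseline summaries, and Protocol 9.7.6 flags critically significant changes in laboratory and ECG values and vital signs. This stands. A reader might infer that ECG and laboratory results have no link to baseline at all, and the SAP contradicts that. The gap is confined to their categories.
- **Adverse events.** Protocol 10.5.1 counts clinically significant worsening of a pre-existing condition, and clinically significant abnormal laboratory findings, as adverse events. SAP 7.1 tabulates events that start or worsen from the first dosing day. This stands in large part, so the documents do not support saying that dizziness or somnolence would be missed. But an examination finding reaches those tables only through the investigator's judgment that it is an event, so they are not an independent summary of the examination.
- **Listings.** With about 10 children per cohort, sorted by subject, parameter and date, each child can be traced by eye. True, but no count results, and no flag is stated for the examination listings.
- **Baseline rates.** A reader might infer that most children start abnormal and that neurological counts sit at a ceiling. No baseline examination rate is given; the protocol describes PCDH19 impairment as varying in degree, and a component-level table need not be at ceiling throughout. For ECG and laboratory, exclusions 7 and 9 make clinically significant abnormality at entry unlikely. With b = 0, the by-visit count is itself the number newly abnormal at that visit.
- **Limits of the remedy.** A shift table cannot show worsening within the abnormal category, and a worst value over several visits raises the count with no control arm to calibrate it. Both are right and shape the fix.

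**Conclusion.** The point holds in limited form. For examination components, the ECG interpretation and laboratory categories, the planned tables cannot give the number of children who became newly abnormal. At n = 10, an unchanged count of 5 fits 0 to 5 new abnormalities. The bounds are exact for any assumed counts. The masking percentages (4% to 91% across the cases tried) rest on assumed rates of onset and resolution and show only that masking ranges from rare to usual.

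The documents do not support the stronger statement that new abnormalities are cancelled or hidden. They can be, in the summary tables; listings and adverse event tables recover part of the information.

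The weight falls on the physical and neurological examinations. It is smaller for laboratory and ECG categories, where numeric change is summarized and entry criteria limit significant abnormality. The SAP cites protocol Amendment 8.1, whereas the protocol text reviewed is dated April 2016. I assume its adverse event definition and dose-escalation visit procedures carry over; the SAP repeats the visit schedule. This is a cheap improvement worth making, not a flaw that undermines the safety analysis.

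**What to change.** In SAP 7.3.2, add for each examination component a table of baseline category by worst post-baseline category within the period, by cohort and overall. Include unscheduled and dose-escalation visits. State the number newly abnormal over the number normal at baseline who have a post-baseline assessment.

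For children already abnormal on a component at baseline, list the baseline and worst post-baseline findings side by side, because the shift table cannot show worsening there.

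Then do the same for the ECG interpretation in SAP 7.3.3 and the laboratory categories in 7.2. In the 26-week period the ECG normally has one post-baseline reading, at Visit 4, so that table is simple. The vital-sign categories in 7.3.1 have the same gap and can take the same table. SAP 9 already repeats the safety tables for the extension.

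The cost is SAP wording and a few standard tables from data already collected. Cells will be sparse in cohorts of about 10. A worst value taken over several visits counts at least as many abnormalities as any one of those visits, so keep the by-visit counts and show the two together.

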7.3.3 ECG

The 12-lead ECG parameters including value and changes from baseline will be summarized using descriptive statistics. ECG results were interpreted as normal, abnormal (not clinically significant) or abnormal (clinically significant). The number and percentage of subjects of each category will be summarized by baseline and post-baseline visit.

Subject listing will be provided. SI units will be used for both summarization and data listings. The critically significant abnormalities will also be flagged in data listings.

7.3.4 EEG

The EEG results will be listed.

7.3.5 C-SSRS

The C-SSRS data will be summarized and listed for each question by visit.

8. OTHER ASSESSMENTS

Visual Analog Scale of Targeted Behaviors will be summarized descriptively for each visit and for change from baseline by cohort.

Blood samples were drawn at baseline, and at Visits 5 and 7 for measurements of concomitant AED and neurosteroid levels, and at Visits 5 and 7 for measurement of study drug serum levels. A listing will be provided to present the serum sample collection status.

9. ANALYSIS OF OPEN-LABEL EXTENSION PERIOD

Baseline for the OLE period is the same as for the main period. The key background and efficacy tables to be provided for the main 26-week open-label treatment period of the study will also be provided for the 52-week OLE. These include:

- Subject disposition
- Demographics and baseline characteristics
- Concomitant non-AED medications and AED medications
- 28-day total seizure frequency for the sum of individual seizures and clusters
- Percentage of both individual seizure free and cluster free days

All of the safety tables provided for the main 26-week open-label period will also be provided for the 52-week OLE.

The concomitant medications summary will include only those medications taken during the OLE period; i.e., those taken on or after the first dosing day of the OLE period and, for those subjects who enter the extension of the OLE, before the first dosing day of that extension.

The seizure endpoints will be based on both 6 and 12 months of OLE experience. The 6-month endpoints will be derived based on the first dosing day of OLE treatment through the last day of OLE treatment or 6 months of OLE treatment, whichever is earlier. The 12-month endpoints will be derived based on the first dosing day of OLE treatment through the end of the study, or if the subject enters the extension of the OLE, through the last day of OLE treatment.

Only the MITT population will be used for the efficacy analyses.

The adverse events will be summarized over just the OLE period as well as over the entire study (26-week main study and OLE periods). The summarizations over just the OLE period will include only those AEs that start or worsen on or after the first dosing day of GNX in the OLE period and, for subjects who enter the extension of the OLE period of the study, before the first

dosing day of that extension. The summarizations over the entire study will include AEs that start or worsen on or after the first dosing day of GNX and, for subjects who enter the extension of the OLE period of the study, before the first dosing day of that extension. Just the TEAEs will be summarized; there will be no table of pre-treatment emergent AEs.

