9.4.4 Study Dosing and Dosage Adjustments For subjects >30 kg

After Sponsor and Principal Investigator have reviewed subject's history, baseline seizure data and inclusion/exclusion criteria and determined a subject to be eligible for the study, ganaxolone treatment will be initiated at a dose of 900 mg/day in divided doses. The dose will be increased by approximately 20 to 50% (e.g., an increase from 900 mg/day to 1200 mg/day is a 33% increase) at intervals of not less than 3 days and not more than 2 weeks provided current dose is reasonably tolerated, until desired efficacy is achieved or a maximally tolerated dose (MTD) level is reached. Subsequent dose adjustments should

be made in increments of approximately 20 to 50% with a minimum of three days between dose changes, unless required for safety. Any and each dose escalation above 1500 mg/day requires a clinic visit scheduled 4-6 days after the dose increase to assess safety and tolerability. The maximum allowable dose is 1800 mg/day.

For subjects ≤30 kg

For children weighing 30 kg (66 lbs) or less, dosing should start at 18 mg/kg/day and be increased in ~20-50% increments at intervals of not less than 3 days and not more than 2 weeks provided current dose is reasonably tolerated, until desired efficacy is achieved or a maximally tolerated dose (MTD) level is reached. Subsequent dose adjustments should be made in increments of ~20-50% with a minimum of three days between dose changes, unless required for safety. Any and each dose escalation above 54 mg/kg/day requires a clinic visit scheduled 4-6 days after the dose increase to assess safety and tolerability. The maximum allowable dose is 63 mg/kg/day. (see Appendix 4 for suggested dose escalation schedule.)

DOWN TITRATION

At the conclusion of the study, or upon discontinuation if the subject is terminated from the study prior to Week 26, a period of down-titration from 1 to 4 weeks should be initiated. The down-titration duration will be determined by the site investigator with input from the Sponsor based on subject's age, weight, dose and duration on study medication.

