9.5.5.9 Visit 9 (end of Week 62 +/-14 days)

- Review background AEDs and other concomitant medications
- Collect and review seizure calendars; provide new calendars
- Complete CGII-Clinician rating
- Collect CGII-Patient/Caregiver rating
- VAS
- Perform physical and neurological examinations
- Assess for adverse events
- Measure vital signs
- Draw blood sample for trough study drug, hematology, chemistry, and allopregnanolone, related endogenous CNS-active steroids; obtain urine sample from subjects who are toilet trained for urinalysis and pregnancy test for WCBP.
- EEG
- Administer Columbia Suicide Scale assessed for children 7 years and older
- Collect bottles from prior visit study medication
- Dispense study medication

- 9.5.5.10 Visit 10 (end of Week 78 +/- 14 days; final investigative visit)
 - Review background AEDs and other concomitant medications
 - Collect and review seizure calendars; provide new calendars
 - Complete CGII-Clinician rating
 - Collect CGII-Patient/Caregiver rating
 - VAS
 - Perform physical and neurological examinations
 - Assess for adverse events
 - Measure vital signs
 - Draw blood sample for trough study drug, hematology, chemistry, and allopregnanolone, related endogenous CNS-active steroids; obtain urine sample from subjects who are toilet trained for urinalysis and pregnancy test for WCBP.
 - EEG
 - Administer Columbia Suicide Scale assessed for children 7 years and older
 - Collect bottles from prior visit study medication
 - Instruct on down-titration
 - Dispense study medication
- 9.5.5.11 Visit 11 (end of Week 82 +/-7 days; Post-Drug Follow up visit)
 - Review background AEDs and other concomitant medications
 - Collect and review seizure calendars
 - Assess for adverse events
 - Measure vital signs
 - EEG
 - Administer Columbia Suicide Scale assessed for children 7 years and older
 - Collect bottles from prior visit study medication
 - Provide information on follow up care

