- 5 Adjust dose if necessary.
- 6 If this is the last study visit, the subject should be instructed on down-titration and schedule for the Follow-up Visit (V11) when down titration has been completed.
- 7 Not applicable for subjects who continue GNX dosing after completing the 52 week OLE.

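### SAP Section 9 leaves the 12-month extension seizure window open to taper and post-drug days for children who stop ganaxolone, but not for those who continue

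*SAP*

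**What the plan says.** SAP Section 9 defines the OLE seizure endpoints over 6 and 12 months.

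- **6 months, all children:** from the first OLE dosing day "through the last day of OLE treatment or 6 months of OLE treatment, whichever is earlier".
- **12 months, children who do not enter the further extension:** to the end of the study, which is the first limb of the rule "first dosing day of OLE treatment through the end of the study, or if the subject enters the extension of the OLE".
- **12 months, children who do enter it:** "if the subject enters the extension of the OLE, through the last day of OLE treatment".

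The seizure tables listed there are 28-day total seizure frequency and the percentage of days free of both individual seizures and clusters. SAP Section 6.1 divides counts by all days with available diary data in the period. It has no rule that separates full-dose, taper and post-drug days.

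Diary recording goes on after the OLE ends. At Visit 10 (Protocol Section 9.5.5.10) staff are to "Collect and review seizure calendars; provide new calendars", instruct on down-titration and dispense medication. Protocol Section 9.4.4 says that "a period of down-titration from 1 to 4 weeks should be initiated". The next contact is "Visit 11 (end of Week 82 +/-7 days; Post-Drug Follow up visit"), where calendars are collected again (Section 9.5.5.11). SAP Table 2, footnote 7, marks that visit "Not applicable for subjects who continue GNX dosing after completing the 52 week OLE".

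**The concern.** One paragraph uses two different end dates for the same 12-month endpoint, and a child's end date depends on whether the child goes on with ganaxolone. SAP Section 1.3.1 reserves continuation for children who still benefit, so the split follows outcome. If the end of the study means Visit 11, the rate for a child who stops is averaged over days on a reduced dose and days on no drug, while the rate for a child who continues is not.

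Two readings of the OLE tables would suffer. Stoppers would look worse than continuers partly because of the window, on top of the real selection between them. A child who stops early could also have a poorer 12-month value than 6-month value although no further full-dose treatment was given in between. The cohorts were planned at up to 10 children each (SAP Section 1.3.3), and only children with at least a 35% improvement enter the OLE, so a few such children can move a cohort mean.

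**Working it through.** **Timeline.** The documents' own totals reproduce. Maximum participation is 12 (baseline) + 26 + 52 + 4 (down-titration) = 94 weeks, as stated. Visit 11 falls at 26 + 52 + 4 = Week 82, as stated. The nominal gap from Visit 10 (Week 78) to Visit 11 is therefore 4 weeks, or 28 days.

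**Off-drug time in that gap.** The taper of 1 to 4 weeks lies inside the gap. Nominal off-drug time is 4 minus the taper length: 3 weeks after a 1-week taper, 0 weeks after a 4-week taper. The 7-day tolerance on Visit 11 makes this 14 to 28 days and 0 to 7 days respectively.

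**Share of the window.** For a 52-week completer the 28 days are 28/(364 + 28) = 7.1% of the 12-month window. For a child who stops at OLE week 8 they would be 28/(56 + 28) = 33.3%. The 28 days after an early stop are an assumption, because the SAP schedules Visit 11 for when down-titration is complete and gives no fixed interval.

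**Effect on the reported value.** The documents give no seizure rates during or after the taper. I assume a true 50% reduction while the drug acts and the baseline rate otherwise. With E weeks under drug effect and N weeks at the baseline rate:

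reported change = (0.5 × E + N)/(E + N) − 1

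| What happens in the 28 days | 52-week completer | Stops at OLE week 8 |
|---|---|---|
| 4-week taper, effect retained | (0.5×56 + 0)/56 − 1 = −50.0% | (0.5×12 + 0)/12 − 1 = −50.0% |
| 1-week taper with effect retained, then 3 weeks off drug | (0.5×53 + 3)/56 − 1 = −47.3% | (0.5×9 + 3)/12 − 1 = −37.5% |
| No effect on any of the 28 days | (0.5×52 + 4)/56 − 1 = −46.4% | (0.5×8 + 4)/12 − 1 = −33.3% |

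A child who continues has no such days and shows −50% in every row. Seizure rates above baseline after stopping would widen the differences.

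**6 against 12 months in the same child.** Take the week-8 stopper with the 1-week taper. The 6-month window excludes post-drug days, so it gives −50% whether it ends after 8 weeks (4/8 − 1) or after 9 (4.5/9 − 1). The 12-month window, if it runs to Visit 11, gives −37.5%. The difference comes from the three post-drug weeks alone.

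**The case against.** A reader might infer that the SAP plainly counts taper and off-drug days as treatment for stoppers. The documents do not settle that, and several places point the other way.

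- Protocol Section 6 has children down-titrated at the end of the study or at discontinuation, and Section 9.4.4 starts the taper at the study's conclusion. Section 9.5.5.10 labels Visit 10 the final investigative visit. On that usage a completer's window closes before the taper.
- SAP Section 2.1 limits tables to events within the respective period, Section 1.3.1 lists the 52-week OLE and the down-titration as separate components, and 56 weeks is more than 12 months of OLE experience.
- The separate clause for continuers may exist only because their study does not end with the OLE.

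A reader might also assume four weeks off drug after the last dose. The schedule does not support that: the taper takes up 1 to 4 of those weeks, so −46% and −33% are the limit of no effect on any taper day.

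These points reduce the certainty and the size, but they do not remove the problem. The narrow reading does not explain why the same paragraph uses the last day of OLE treatment for everyone at 6 months and a different term at 12. The protocol wording that places the end of the study before the taper names discontinuation separately, so it gives no end date for a child who stops partway through the OLE. The SAP also cites Protocol Amendment 8.1 of August 2017, whereas the protocol reviewed is dated April 2016. A definition could stand in that amendment, but the SAP does not point to one.

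It is also fair to say that Section 9 specifies no formal comparison of 6 with 12 months or of stoppers with continuers, and that counting these days would tend to understate benefit.

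**Conclusion.** The point holds as an undefined and unequal window, not as a demonstrated bias. The 12-month rule has two end dates. For stoppers one of them can be read to include taper and post-drug days, and nothing in the SAP excludes those days. For continuers it cannot.

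On the stated assumptions the distortion is at most about 4 percentage points for a 52-week completer and about 17 for a child stopping at OLE week 8. It is zero in both if the effect lasts through a 4-week taper, and zero for a completer if the window closes at Visit 10. The documents do not say how many children stop early, so the effect on a cohort summary cannot be estimated. The tables concerned are descriptive OLE summaries in an uncontrolled study, and the 26-week primary endpoint is untouched. It is worth correcting because the artefact would follow outcome and the correction is simple.

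**What to change.** Replace the two end dates in SAP Section 9 with one rule for every child and for both windows: from the first OLE dosing day to the last day of OLE treatment before down-titration begins, capped at 6 or 12 months. The reference to down-titration is needed. Taper days are dosing days, so the last day of OLE treatment on its own could still take in the whole taper for stoppers and none for continuers, and the present 6-month rule has the same gap. Summarise seizures during the taper and post-drug follow-up separately, by cohort.

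This is a change of a clause or two, with no new data and no change to conduct. The price is slightly fewer diary days for stoppers, and a few days lost at the cap where Visit 10 falls late in its 14-day tolerance. The start of down-titration must be available as a date for each child who stops.
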